4.2.2. Handling of Withdrawals

If a patient discontinues study treatment but remains on study, every effort should be made to continue the patient's assessments according to the schedule of assessments (Section) through the end of the study. For patients who withdraw from the study, procedures and assessments for the end-of-treatment (EOT) visit (Section 6.1.3) should be performed at the time of discontinuation of treatment or as soon as possible thereafter (unless the patient withdraws consent to do so). A follow-up assessment performing end of treatment (EOT) procedures should be undertaken 4 weeks after discontinuation of study treatment.

If a patient fails to return for scheduled visits, a documented effort must be made to determine the reason. If the patient cannot be reached by telephone, a certified letter should be sent to the patient (or the patient's legally authorized representative, if appropriate) requesting contact with the investigator. This information should be documented in the study records.

Before enrollment into the study, the investigator or designee must explain to each patient that for evaluation of study results, the patient's protected health information obtained during the study may be shared with the study sponsor, regulatory agencies, and IRB/independent ethics committee (IEC). It is the investigator's (or designee's) responsibility to obtain written permission to use protected health information per country-specific regulations, such as the Health Insurance Portability and Accountability Act (HIPAA) in the US, from each patient, or if appropriate, the patient's legally authorized representative. If permission to use protected health information is withdrawn, it is the investigator's responsibility to obtain a written request, to ensure that no further data will be collected from the patient, and the patient will be removed from the study.

Upon occurrence of a serious or intolerable AEs, the investigator will confer with the Sponsor. It is vital to obtain follow-up data on any patient withdrawn because of an AE or serious AE (SAE). In every case, efforts must be made to undertake protocol-specified, safety follow-up procedures.

Notification of early patient discontinuation from the study and the reason for discontinuation will be made to the sponsor, and will be clearly documented on the appropriate electronic case report form (eCRF).

4.2.3. Replacements

There will be no replacements in this study.

5. Study Treatments

5.1. Method of Assigning Patients to Treatment

Once the investigator confirms that the patient has met all eligibility criteria, the patient will be enrolled in the study by the local investigators and their teams. Trial treatment should begin on the day of enrollment or as close as possible to the date on which the patient is enrolled. The investigator is responsible to maintain appropriate records and ensure appropriate supply, storage, handling, distribution and usage of trial treatments is in accordance with the protocol and any applicable laws and regulations.

5.2. Treatments Administered

Refer to Table 8 (Schedule of Assessments) for additional details.

5.2.1. Galinpepimut-S

Each of the 4 peptides will be supplied at a concentration of 0.2 mg/vial. After reconstitution with 0.6 mL sterile water for injection (SWFI), each peptide will be at a concentration of 0.4 mg/mL (400 µg/mL of each peptide) combined in a single sterile solution in a buffer consisting of 10 mM histidine, pH 6.0 + 0.05% ethylene diamine tetra acetic acid (EDTA). As galinpepimut-S will comprise 50% (0.5 mL) of the study treatment injection administered, the actual dose of each peptide is 200 µg (with the total 4 active peptides equaling 800 µg). On galinpepimut-S administration days, blood samples will be collected before study treatment administration. Before injection, study staff will assess the immunization site. Patients will receive an injection of GM-CSF (refer to [Section 5.2.3](#)).

A 1-mL dose of galinpepimut-S will be administered subcutaneously (SC) on the arm, leg, or torso of the patient, and should be positioned at least 5 cm away from the previous site of the study treatment injection.

A maximum of 16 total injections will be administered as follows:

- First 2 galinpepimut-S injections: every 3 weeks (×2). Thereafter, galinpepimut-S will also be administered every 3 weeks to coincide with pembrolizumab treatment as detailed below:
- Injections 3 to 6: every 3 weeks (between Weeks #6 and #15). The first series of 6 injections of galinpepimut-S (I + II) define the initial immunization induction phase.
- Injections 7 to 12: every 3 weeks (between Weeks #21 and #36). The second series of injections of galinpepimut-S define the early immune booster phase.
- Injections 13 to 18: every 12 weeks (between Weeks #48 and #84). The series of the last 4 injections of galinpepimut-S define the late immune booster phase.
- As galinpepimut-S will be co-administered with Montanide, specific information about this emulsifying agent is provided in the Montanide Investigator Brochure.

Every effort should be made to follow the administration schedule for galinpepimut-S and pembrolizumab. If a patient misses a scheduled administration of either the combination or pembrolizumab alone, the drug(s), should be administered as soon as possible. If the patient is more than one-half the time interval to the next scheduled administration, the patient should skip that preplanned administration and have the next administration on schedule.

Galinpepimut-S will be administered 30-60 minutes after the completion of IV infusion of pembrolizumab on Day 1 of each cycle during which the 2 drugs are being co-administered.

Refer to [Section 5.2.2](#) for Montanide ISA 51 VG administration.

5.2.2. Montanide ISA 51 VG

Galinpepimut-S treatment preparation will require reconstitution of the lyophilized powder with SWFI, followed by a mixture of the peptide solution of galinpepimut-S with the

immunologic adjuvant Montanide ISA 51 VG as an emulsion to a total volume of 1 mL. The study treatment solution will comprise 50% (0.5 mL) of galinpepimut-S and 50% (0.5 mL) Montanide.

Galinpepimut-S includes concomitant administration of Montanide (adjuvant) on Day 1 of all sessions of administration of this direct immunizer.

Galinpepimut-S will be subsequently mixed in a water-in-oil emulsion with the oily adjuvant Montanide ISA 51 at a 1:1 ratio. The resulting final emulsion will be administered to the patient SC as a 1 mL injection.

5.2.3. Sargramostim (GM-CSF)

Patients will receive 70 µg sargramostim (GM-CSF) SC on Day -2 and on Day 1 before each galinpepimut-S injection. Patients will remain in the clinic for approximately 30 minutes following receipt of GM-CSF. This injection will occur at the same anatomical site of the next planned study treatment injection.

5.2.4. Pembrolizumab

Treatment for pembrolizumab is outlined below in [Table 2](#).

Table 2 Treatment with Pembrolizumab (irrespective of whether it is administered alone or concomitantly with galinpepimut-S)

Drug	Dose/Potency	Dose Frequency	Route of Administration	Regimen	Use
Pembrolizumab	200 mg	Every 3 weeks	Intravenous	Day 1 of each cycle (3 week cycles) and begins at Week 6	Experimental

Pembrolizumab will be administered as a dose of 200 mg using a 30-minute IV infusion. Sites should make every effort to target infusion timing to be as close to 30 minutes as possible. However, given the variability of infusion pumps from site to site, a window between -5 minutes and +10 minutes is permitted (i.e., infusion time is 30 minutes -5 min/+10 min).

The Pharmacy Manual contains specific instructions for the preparation of the pembrolizumab infusion and administration of infusion solution.

Patients can receive up to 35 treatments (approximately 2 years) with pembrolizumab. During that time, patients may continue until disease progression, unacceptable toxicity, withdrawal of consent, physician's decision to stop therapy for the patient, or Sponsor's decision to terminate the study.

Discontinuation of treatment may be considered for patients who have attained a confirmed CR (either solid tumors or AML, using the corresponding response definitions), as follows: Such patients would have attained CR after having been treated for **at least** 10 cycles of galinpepimut-S, i.e., at least 30 weeks: 2 cycles of galinpepimut-S monotherapy (6 weeks) followed by 9 cycles of pembrolizumab (an additional 24 weeks). Such patients in CR should also receive 2-additional cycles of the combination (2 doses of pembrolizumab and galinpepimut-S [until Week 36]) beyond the date when the initial CR was declared, so that at least 12 of the total 16 (75%) planned doses of galinpepimut-S would have been administered. At that time, 12 out of a planned total of 36 treatments (2 years) with pembrolizumab (corresponding to approximately 33% of the total planned pembrolizumab treatments).

Note: The number of treatment administrations is calculated starting with the first dose of galinpepimut-S.

5.3. Identity of Investigational Drug Product

Table 3 provides a description for each of the investigational products.

Table 3 Description of Investigational Products

Product	Supplied as:
Galinpepimut-S	0.8 mg sterile, white preservative-free powder filled into a 2-mL colorless glass vial provided by the sponsor. Lyophilized galinpepimut-S requires reconstitution with sterile water (not provided by the sponsor)
Montanide ISA 51 VG	3-mL amber glass vial provided by the sponsor
Sargramostim (GM-CSF)	250-µg sterile, white, preservative-free powder in a single-use vial provided by the sponsor. Lyophilized sargramostim requires reconstitution with sterile water (not provided by the sponsor)
Pembrolizumab	Solution for infusion is supplied by the sponsor as 100 mg/vial liquid DP (manufactured using the fully formulated DS with L-histidine as a buffering agent, polysorbate 80 as a surfactant, and sucrose as a stabilizer/tonicity modifier) in a single use glass vial (will be provided by Merck).

Abbreviations: GM-CSF, granulocyte-macrophage colony-stimulating factor; USP, United States Pharmacopeia.

5.3.1. Galinpepimut-S

Galinpepimut-S is a lyophilized preparation of 4 different WT1-derived synthetic analog peptides considered as a multicomponent single drug product. Each of the 4 peptides will be supplied at a concentration of 0.2 mg/vial. After reconstitution with 0.6 mL SWFI, each peptide will be at a concentration of 0.4 mg/mL (400 µg/mL of each peptide) combined in a single sterile solution (after reconstitution into liquid/soluble form) in a buffer consisting of

Peptide abbreviations: A, alanine; C, cysteine; D, aspartic acid; E, glutamic acid; F, phenylalanine; G, glycine; H, histidine; K, lysine; L, leucine; M, methionine; N, asparagine; P, proline; Q, glutamine; R, arginine; S, serine; T, threonine; V, valine; Y, tyrosine. *Designates single amino acid substitution (R>Y) by deliberately designed mutations in the heteroclitic peptides

The Drug Substance for the 4 peptides are manufactured at Polypeptide Laboratories, Inc. (Torrance, CA, USA). The lyophilization process, manufacturing of Drug Product (API) and sterile fill and finish under Good Manufacturing Practice conditions are performed by Corden Pharma S.p.A. (Caponago, Italy). Each lot of the lyophilized peptide powder are tested for physicochemical stability, sterility, and API content at PPD GMP Laboratories, Inc. (Middleton, WI, USA).

Galinpepimut-S is considered as a multicomponent single drug product comprised of 4 peptides (described above) in a sterile lyophilized powder containing 0.8 mg peptides. Galinpepimut-S will be provided as a sterile, white, preservative-free powder filled into a 2 mL vial, for reconstitution with 0.6 mL SWFI. After reconstitution with SWFI, the peptides will be in a buffer of 10 mM histidine, pH 6.0 + 0.05% EDTA. Galinpepimut-S will be mixed in a water in oil emulsion with the oily adjuvant Montanide at a 1:1 ratio. The resulting final emulsion, which is administered as study treatment, will also be referred to as galinpepimut-S for practical product administration purposes in this protocol.

The total amount of the finished product is 0.96 mg (overfill of 20%) filled into a 2-mL colorless glass vial. The vial should be stored at the site at or below -20°C until use.

5.3.2. Montanide ISA 51 VG

Montanide ISA 51 VG is an adjuvant (NSC # 737063) produced by SEPPIC, Inc. (Fairfield, NJ) under Good Manufacturing Practice and is composed of a light oil and a surfactant system designed to make a water-in-oil emulsion. Montanide ISA 51 VG has been clinically tested based on a vegetable grade formulation used to emulsify the peptides. Montanide ISA 51 VG has proved to be a very efficient adjuvant, activating the cellular and the humoral

immune response. Montanide ISA 51 VG has been administered to more than 10,000 patients throughout the world. Montanide is packaged in 3-mL amber glass vials. The adjuvant is stored between 15°C to 30°C and must not be frozen.

5.3.3. Sargramostim (GM-CSF)

Sargramostim (GM-CSF) is manufactured by Partner Therapeutics, Inc. (Lexington, MA), under Good Manufacturing Practices and is provided in lyophilized form as a 250-µg sterile, white, preservative-free powder that requires reconstitution with SWFI. GM-CSF must be stored at 2°C to 8°C. For this study, the vial of GM-CSF is intended for single-use only.

5.3.4. Pembrolizumab

The pembrolizumab treatment to be used in this trial is outlined in Table 2 in Section 5.2.4. above.

5.3.5. Overall Treatment Schedule

The overall treatment administration schedule is shown in [Figure 13](#) below:

Less likely:

- Arthralgias, myalgias
- Fever
- Headache
- Edema
- Allergic reaction

Rare:

- Elevated liver function tests
- Elevated kidney function tests
- Shortness of breath

Montanide ISA 51 VG: The potential toxicities/side effects of Montanide ISA 51 VG include:

- Mild inflammation at injection sites
- Occasional fever
- Allergic reactions have been observed rarely

Sargramostim (GM-CSF): Sargramostim is an approved product, available in the US since 1991. It has been used in a number of studies as an immunologic adjuvant with the presumed benefit mediated through effects on dendritic and other antigen-presenting cells. Several human vaccine studies in melanoma and other human malignancies have reported both

encouraging immunologic and clinical results. More recently, 2 melanoma vaccine studies have reported a harmful effect of GM-CSF when used as a vaccine adjuvant ([Faries et al, 2009](#); [Slingluff et al, 2009](#)). While it is important to recognize a potential negative effect, this study uses a different vaccine with a different dose of GM-CSF in a different disease.

The potential toxicities/side effects of GM-CSF include (at standard doses of 250 $\mu\text{g}/\text{m}^2/\text{day}$ for 5 to 14 days):

- Edema
- Fluid retention
- Headache
- Myalgia
- Arthralgia
- Dyspnea
- Allergic reactions
- Patients with pre-existing renal and/or hepatic disorders may demonstrate elevations in serum creatinine or bilirubin/transaminases, respectively.

Pembrolizumab toxicities are detailed in [Section 5.3.6.3.1](#).

5.3.6.1. Dose-Limiting Toxicities

All toxicities will be graded using National Cancer Institute Common Terminology Criteria for Adverse Events (NCI CTCAE) Version 5.0, (published in November 2017), as per the following link:

https://ctep.cancer.gov/protocolDevelopment/electronic_applications/docs/CTCAE_v5_Quick_Reference_5x7.pdf.

For patients enrolled across all active solid tumor cohorts (colorectal, ovarian, small cell lung cancer, breast cancer), the dose-limiting toxicity (DLT) window of observation will be at least one (1) cycle following the co-administration of galinpepimut-S in combination with pembrolizumab. A DLT is judged by the investigator to be possibly, probably, or definitely related to study drug administration. AML-specific DLTs will be considered separately ([Section 5.3.6.2](#)).

The occurrence of any of the following toxicities will be considered a DLT (except for AML; please see [Section 5.3.6.2](#)), if judged by the investigator to be possibly, probably, or definitely related to study drug administration:

1. Grade 4 nonhematologic toxicity (not laboratory)
2. Grade 4 hematologic toxicity lasting ≥ 7 days, except thrombocytopenia:
 - Grade 4 thrombocytopenia of any duration
 - Grade 3 thrombocytopenia associated with bleeding
3. Any nonhematologic AE \geq Grade 3 in severity should be considered a DLT, with the following exceptions: Grade 3 fatigue lasting ≤ 3 days; Grade 3 diarrhea, nausea, or vomiting without use of anti-emetics or anti-diarrheals per standard of care; Grade 3 rash without use of corticosteroids or anti-inflammatory agents per standard of care.
4. Grade 3 nonhematologic toxicity (not laboratory) lasting > 3 days despite optimal supportive care.
5. Any Grade 3 or Grade 4 nonhematologic laboratory value if:

- Clinically significant medical intervention is required to treat the patient, or
 - The abnormality leads to hospitalization, or
 - The abnormality persists for > 1 week.
 - The abnormality results in a drug-induced liver injury (DILI)
 - Exceptions: clinically nonsignificant, treatable, or reversible laboratory abnormalities, including liver tests, uric acid, etc.
6. Febrile neutropenia (FN) Grade 3 or Grade 4:
 - Grade 3 is defined as absolute neutrophil count (ANC) < 1000/mm³ with a single temperature of > 38.3°C (101°F) or a sustained temperature of ≥ 38°C (100.4°F) for more than 1 hour
 - Grade 4 is defined as ANC < 1000/mm³ with a single temperature of > 38.3°C (101°F) or a sustained temperature of ≥ 38°C (100.4°F) for more than 1 hour, with life-threatening consequences and urgent intervention indicated.
 7. Any treatment-related toxicity that causes the patient to discontinue treatment during the period from the first administration of galipepimut-S until the completion of the first cycle of galipepimut-S plus pembrolizumab combination therapy.
 8. Missing > 25% of pembrolizumab doses as a result of drug-related AE(s) during the first cycle of combination therapy.
 9. Thrombocytopenia < 25,000/mm³ if associated with:
 - A bleeding event which does not result in hemodynamic instability but requires an elective platelet transfusion, or
 - A life-threatening bleeding event which results in urgent intervention and admission to an Intensive Care Unit (ICU)
 10. Prolonged delay (> 2 weeks) in initiating Cycle 2 of combination therapy due to treatment-related toxicity
 11. Grade 5 toxicity.

Missing > 25% of the doses of either investigational agent as a result of drug-related AE(s) during the period from first administration of galipepimut-S and up until the completion of

the first cycle of the co-administration of galinpepimut-S in combination with pembrolizumab.

Staggered Early Enrollment:

To minimize exposing subjects to the risk of potential unknown acute and subacute toxicities of combining pembrolizumab with galinpepimut-S, the inter-dosing interval in-between the first consecutive three (3) subjects to be enrolled in this study arm will be one (1) week following the administration of the first dose of pembrolizumab in these patients.

DLT assessment and actions will be as follows (unless stopping rules apply):

- If 2 or fewer patients of these first 6 patients have DLTs, enrollment can continue for up to another 6 patients across these arms with no dose adjustments made. If DLTs are observed in more than 2 patients of the first 6, the time interval between galinpepimut-S doses for the inoculation following the one associated with the DLT will be doubled. For example, if galinpepimut-S was given on a Q3W schedule before the DLT occurred, it should be given Q6W for the immediately subsequent administration after the dosing event associated with the DLT, while keeping the pembrolizumab dose and frequency stable.
- In the next 6 patients (patients 7 to 12), if again, 2 or fewer of these patients have DLTs observed, enrollment can continue. If DLTs are observed in more than 2 of patients 7 to 12, the time interval between galinpepimut-S doses for the inoculation following the one associated with the DLT will be doubled, , but pembrolizumab will continue as scheduled.
- If DLTs are observed in more than 2 patients of the first 6 (patients 1 to 6) and again in more than 2 patients of the next 6 (patients 7 to 12), the time interval between galinpepimut-S doses will be doubled for two (2) inoculations following the one associated with the DLT. For example, if galinpepimut-S was given on a Q3W schedule before the DLT occurred, it should be given Q6W for the 2 immediately subsequent administrations after the dosing event associated with the DLT, while keeping the pembrolizumab dose and frequency stable.

- If DLTs continue to be observed above 2 per every 6 patients beyond these first 12 patients, and even after the changes in administration of galinpepimut-S, the study will be stopped and the safety data will be examined by the sponsor in consultation with investigators in order to determine how to proceed or whether to discontinue the study.
- Should a given patient experience any of the above DLTs at any time after the completion of the first cycle of co-administration of galinpepimut-S in combination with pembrolizumab, the time interval between galinpepimut-S doses for the inoculation following the one associated with the DLT will be doubled, but pembrolizumab will continue as scheduled.
- If another DLT occurs in that next cycle, the time interval between galinpepimut-S doses will be doubled for two (2) inoculations following the one associated with the DLT, but pembrolizumab will continue as scheduled.
- If no DLTs re-occur after the above periods of doubly 'spaced out' administrations, then the patient should revert back to the initial GPS Q3W schedule (as per the initial dosing frequency/ investigational agent administration schedule).
- If a DLT occurs after these dose modifications in subsequent cycles, the patient will be discontinued from the study.

The above dose density modifications in response to DLTs is further summarized in the bulleted list of actions below:

- First DLT → skip the next GPS inoculation (scheduled for the next cycle, i.e., 3 wks ahead) and administer GPS 6 wks ahead (i.e., 'spread out') **once thereafter**, i.e. **for 1 additional cycle** → DLT resolution → Return to per protocol schedule of GPS administration
- Second DLT (after reverting to the per protocol schedule) → skip the next GPS inoculation (scheduled for the next cycle, i.e., 3 wks ahead) and administer GPS 6 wks ahead (i.e., 'spread out') **twice thereafter**, i.e. **for 2 additional cycles** → DLT resolution → Return to per protocol schedule of GPS administration

- Third DLT (occurring either after reverting to the per protocol schedule or during the ‘spread out’ schedule to manage the 2nd DLT above) → Discontinue patient from study.
- N.B.: In all above modifications of the dose density of galipepimut-S, as all intervals (in weeks) between 2 successive GPS administrations are multiples of three (3) by design, following these rules, co-administration with pembrolizumab is always secured.

Stopping Rules:

- Development of any SAEs at least “possibly attributable” to the study agent(s) in 2 out of the first 6 patients in the study. In this case, the upper 90% one-sided CI bound for 2 patients with SAEs within 6 patients would be 66.7%, consistent with an excessive rate of toxicity.
- The fraction of patients experiencing an SAE at least “possibly attributable” to the study agent(s) exceeds 1/3, at any time during study implementation beyond the first 6 patients.
- Death at least “possibly attributable” to the study agent(s) within 30 days after the administration of the investigational treatment (GPS plus pembrolizumab).

If the study is stopped due to activation of the above rules, the safety data will be examined by the Sponsor in consultation with investigators in order to determine how to proceed or whether to discontinue the study at large.

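### For a DLT up to the end of the first combination cycle, the narrative DLT rules and the bulleted list that summarizes them give different galinpepimut-S instructions

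*Combined protocol and SAP*

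**What the plan says.** For the solid tumor arms, Section 5.3.6.1 sets a DLT "window of observation will be at least one (1) cycle following the co-administration of galinpepimut-S in combination with pembrolizumab". The actions that follow, which apply unless a stopping rule does, come in two layers.

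- **Group rule.** With 2 or fewer DLT patients in the first six, "enrollment can continue for up to another 6 patients across these arms with no dose adjustments made". The other branch begins "If DLTs are observed in more than 2 patients of the first 6, the time interval between galinpepimut-S doses" and doubles the interval for the inoculation after the one associated with the DLT. For patients 7 to 12 the threshold is the same: "if again, 2 or fewer of these patients have DLTs observed, enrollment can continue", and above 2 the interval is doubled. Beyond patient 12, Sections 5.3.6.1 and 5.3.6.2 give only a study-level stop.
- **Per-patient rule.** The interval is doubled for an individual patient on this condition: "Should a given patient experience any of the above DLTs at any time after the completion of the first cycle of co-administration".

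A bulleted list follows, introduced as a summary of the dose density modifications above it. Its first entry tells the site, after a first DLT, to "skip the next GPS inoculation (scheduled for the next cycle, i.e., 3 wks ahead", and to give galinpepimut-S 6 weeks ahead instead. It mentions neither when the DLT occurred nor how many patients are affected.

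The synopsis and Section 5.3.6.2 (AML) have the same two layers and the same list. The AML synopsis, however, starts the per-patient rule after the second co-administration cycle, and Section 5.3.6.2 starts it after the first.

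**The concern.** The first combination cycle is the period that DLT monitoring is mainly meant to cover. A patient who has a DLT in that cycle, or during the preceding galinpepimut-S monotherapy doses, is not yet under the narrative's per-patient rule. The narrative changes that patient's galinpepimut-S interval only through the group count. The list changes it on the patient's own DLT alone.

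Two sites could each follow a part of the protocol faithfully and schedule the same patient's next inoculation differently. That bears on patient safety. It also bears on the DLT data, because later DLT counts would come from patients handled under different rules.

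**Working it through.** The plan states no DLT rate and no operating characteristic for these rules, so there is no figure of its own to reproduce. The check is a comparison of texts, followed by an illustration of how often they diverge.

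**Step 1. The two texts side by side, for a first DLT up to the end of the first combination cycle**

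| Situation | Narrative | Bulleted list |
|---|---|---|
| Patients 1 to 6, at most 2 with DLTs | Enrollment continues; no galinpepimut-S change stated for the affected patient | Next inoculation skipped |
| Patients 1 to 6, more than 2 with DLTs | Next interval doubled | Next inoculation skipped |
| Patients 7 to 12, at most 2 with DLTs | Enrollment continues; no change stated | Next inoculation skipped |
| Patients 7 to 12, more than 2 with DLTs | Next interval doubled (two intervals if the first six also exceeded 2) | Next inoculation skipped |
| Beyond patient 12 | Study-level stop only; no individual change stated | Next inoculation skipped |

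The texts broadly agree only where more than 2 of 6 patients have DLTs. They differ in the other rows.

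**Step 2. Start point in AML.** Section 5.3.6.2 sets a DLT window of 8 weeks from the first galinpepimut-S dose. Co-administration starts at Week 6 in 3-week cycles, so on schedule the first combination cycle ends at Week 6 + 3 = 9 and the second at Week 12. That section's window therefore closes before its per-patient rule begins, and the AML synopsis begins the rule a further cycle later.

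**Step 3. How often the texts differ within a group of six**

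Inputs: group size 6 and threshold of more than 2, both from Section 5.3.6.1. Assumptions: true DLT rate p of 10%, 20% or 33% (computed at 1/3), independent patients, stopping rules ignored.

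Given one patient with an early DLT, let X be the number of the other five with a DLT, X ~ Binomial(5, p). The texts differ when X ≤ 1:

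P(X ≤ 1) = (1 − p)^5 + 5p(1 − p)^4

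- p = 0.10: 0.590 + 0.328 = 0.919, or 92%
- p = 0.20: 0.328 + 0.410 = 0.737, or 74%
- p = 1/3: 0.132 + 0.329 = 0.461, or 46%

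For the group as a whole, the chance that 1 or 2 of 6 have a DLT is 6p(1 − p)^5 + 15p²(1 − p)^4:

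- p = 0.10: 0.354 + 0.098 = 0.453, or 45%
- p = 0.20: 0.393 + 0.246 = 0.639, or 64%
- p = 1/3: 0.263 + 0.329 = 0.593, or 59%

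**Step 4. Effect of the SAE stopping rule.** At least possibly attributable SAEs in 2 of the first six patients stop the study. If every DLT were also such an SAE (an assumption), a second DLT patient would trigger the stop, and the texts would differ in a continuing study only when X = 0. That chance is (1 − p)^5 = 59%, 33% and 13% at the three rates. The Step 3 figures are therefore too high for the first six patients, by an amount that depends on how many DLTs are SAEs.

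**The case against.** Several counter-arguments have force.

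- **The list may summarize only the per-patient bullets just above it.** Its sequence (first DLT, second DLT, return to schedule, discontinuation) matches theirs. On that reading there is a gap, not a contradiction: early DLTs at or below the threshold have no individual galinpepimut-S instruction. But the list states no such limit, so a site may equally read it as general.
- **The phrase about no dose adjustments may describe only the regimen of the next six patients.** This stands. A reader might infer that the narrative orders unchanged dosing for the affected patient, but the text does not clearly say so, and for patients 7 to 12 the phrase is absent. What remains is that no action is stated for that patient.
- **Other provisions act on individuals.** Section 5.3.7 sends certain local and systemic reactions to the medical monitor or takes the patient off treatment. Section 4.2.1 allows removal for a serious or intolerable event, and the stopping rules can halt the study. A reader might infer that an early DLT changes galinpepimut-S only through the count, or that no individual trigger exists. Neither is supported. These provisions do not, however, settle which DLT rule applies.
- **The list need not alter dosing in every case.** A fatal DLT, or one that ends treatment, leaves no next inoculation to reschedule.
- **The gap is not the same as the DLT window.** The solid tumor window is a minimum of one cycle, and the criterion on delayed start of combination cycle 2 can be met after cycle 1, where the per-patient rule already applies.
- **Timing of the count.** A reader might infer that the six-patient count will usually be unknown when the affected patient's next dose is due. The documents give no accrual rate, and more than 2 can be reached before all six patients finish, so this is not established in general.

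**Conclusion.** The inconsistency holds and should be corrected. Up to the end of the first combination cycle, the narrative makes a galinpepimut-S interval change depend on more than 2 of 6 patients, and beyond patient 12 it offers only a study-level stop. The list makes the change depend on the patient's own first DLT. Nothing elsewhere in the protocol reconciles them. The AML synopsis and Section 5.3.6.2 also disagree on when the per-patient rule begins.

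The textual conflict rests on no numerical assumption. The 92%, 74% and 46% are illustrative only: they assume DLT rates the documents do not give, independence between patients and no stopping rule. They should not be read as the proportion of patients who would be handled wrongly.

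**What to change.** Reconcile the DLT action rules in Section 5.3.6.1, Section 5.3.6.2 and the matching synopsis text, so that:

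- the narrative and the bulleted list state the same action, start point and conditions for a DLT during the first co-administration cycle or earlier, including for patients enrolled after the twelfth; and
- the AML synopsis and Section 5.3.6.2 give the same start point for the per-patient rule.

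Which action, start point and conditions apply is a clinical decision for the sponsor and investigators. The cost is protocol wording only, with no extra visits or staff.
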